## 6.2 Key Secondary Efficacy Endpoint and Analysis

## 6.2.1 Key Secondary Endpoint

The key secondary endpoint is change from Baseline to Week 8 in HAM-A Total Score. Analysis of this endpoint will follow the same process as the primary endpoint described in Section 6.1. The outcome for this endpoint will be considered confirmatory, if in agreement with the primary endpoint outcome and provided that the null hypothesis is rejected for the primary outcome. This gatekeeping function of the primary outcome allows for no adjustment of alpha level for multiplicity of testing.

## 6.3 Secondary Efficacy Endpoints and Analyses

All secondary efficacy endpoints will be analyzed on the FAS population. Additional analyses may be performed on the PPS population, where noted.

## 6.3.1 Change from Baseline in HAM-A Total Score

In addition to the primary and key secondary analysis for HAM-A, descriptive statistics will be presented for actual values and change from Baseline for scheduled visits. The change from Baseline will be analyzed using an analysis of covariance (ANCOVA) model including change from Baseline HAM-A Total Score as dependent variable, the baseline HAM-A Total Score as a covariate and treatment group as a fixed effect. The Least Square Means (LS Means) for each treatment group compared to placebo will be reported along with associated 95% CI and p-value. The ANCOVA comparisons will be performed for Week 1, Week 2, Week 4, Week 8 and the End of Study visit and will be presented for both the FAS and PPS populations.

A by-subject listing of results by visit, including any unscheduled visits, will be provided.

## 6.3.2 Change from Baseline in MADRS Total Score

The MADRS consists of 10 questions to assess depression severity and change due to treatment. The questionnaire will be administered by the central rater after completion of the HAM-A. Each question is scored with a range of 0-6 points, with 0 indicating item is not present or is normal, and 6 indicating severe or continuous presence of the symptom. The Total Score, ranging from 0 to 60, is calculated by summing the 10 individual scores. A higher score represents a more severe condition.

Descriptive statistics, including 95% CIs for the mean, will be presented for actual values, change

#### CONFIDENTIAL

and percent change from Baseline for scheduled visits for the FAS. The change from Baseline difference in means between each dose of MM-120 and placebo, 95% CI for the difference and corresponding p value from a two-sample t-test will be presented for Week 1, Week 2, Week 4, Week 8 and the End of Study visit. A by-subject listing of results by visit, including any unscheduled visits, will be provided.

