## 6.3.3 Change from Baseline in CGI-S

The CGI-S assesses the subject's current severity of illness at the time of the assessment, as assessed by the clinician and in reference to the clinician's past experience with patients having the same diagnosis. The CGI-S consists of one investigator-completed rating ranging from 1 (normal, not at all ill) to 7 (among the most extremely ill patients); a higher score indicates a more severe illness.

Descriptive statistics, including 95% CIs for the mean, will be presented for actual values and change from Baseline for scheduled visits. The change from Baseline difference in means between each dose of MM-120 and placebo, 95% CI for the difference and corresponding p value from a two-sample t-test will be presented for Day 2, Week 1, Week 2, Week 4, Week 8 and the End of Study visit. A by-subject listing of results by visit, including any unscheduled visits, will be provided.

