## 6.3.5 Change from Baseline in PGI-S

The PGI-S measures disease severity as a patient reported outcome. The PGI-S consists of one subject-completed rating ranging from 1 (none) - 5 (very severe), where a higher score indicates a more severe illness.

Descriptive statistics, including 95% CIs for the mean, will be presented for actual values and change from Baseline for scheduled visits. The change from Baseline difference in means between each dose of MM-120 and placebo, 95% CI for the difference and corresponding p-value from a two-sample t-test will be presented for Day 2, Week 1, Week 2, Week 4, Week 8 and the End of Study visit. A by-subject listing of results by visit, including any unscheduled visits, will be provided.

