## 6.3.7 Change from Baseline in SDS Total Score

The SDS will assess the extent to which 3 major domains (work, social life/leisure activities, and family life/home responsibilities) are functionally impaired. The SDS is a self-reported assessment with 5 questions. The Total Score is derived as the sum of the response to the first 3 questions, each ranging from 0 (not at all) to 10 (extremely). The Total Score ranges from 0-30, where a higher score indicates increased functional impairment. The last 2 questions are not included in the SDS Total Score.

Descriptive statistics, including 95% CIs for the mean, for the SDS Total Score will be presented for actual values and change from Baseline for scheduled visits. The change from Baseline difference in means between each dose of MM-120 and placebo and 95% CI for the difference will be presented for Week 1, Week 2, Week 4, Week 8 and the End of Study visit. A by-subject listing of results by visit will be provided for all SDS responses and the Total Score.

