## 6.3.8 Change from Baseline in EQ-5D-5L Index Values and VAS

The EQ-5D-5L will assess health outcomes over 5 dimensions: mobility, self-care, usual activities, pain/discomfort, and anxiety/depression and the EuroQol visual analog scale (EQ VAS). Each dimension has 5 levels of response scored as: 1 = no problems, 2 = slight problems, 3 = moderate problems, 4 = severe problems, and 5 = extreme problems. The five dimensions are combined to create a 5-digit code to represent the subject's health state. An EQ-5D-5L index value will be calculated by applying a formula that attaches a weight to each level in each dimension, using the US standard value set. The index is calculated by deducting the appropriate weights from 1, the value of full health. The resulting index value is a number between 0 (equivalent to dead) and 1 (full health). Missing data will not be imputed for analysis.

The frequency and proportion of subjects reporting each level for each of the 5 dimensions will be presented by visit. Changes over time will be presented using figures to present the frequency and proportion of subjects reporting each level for each of the 5 dimensions at baseline and each post-baseline measurement.

The EQ-5D-5L index values will be summarized by descriptive statistics, including 95% CIs for the mean, for actual values and change from Baseline for scheduled visits. The change from Baseline difference in means between each dose of MM-120 and placebo and 95% CI for the difference in means will be presented for Week 4, Week 8 and the End of Study visit.

The EQ VAS will be summarized by descriptive statistics, including 95% CIs for the mean, for actual values and change from Baseline for scheduled visits. The change from Baseline difference in means between each dose of MM-120 and placebo and 95% CI for the difference in means will be presented for Week 1, Week 2, Week 4, Week 8 and the End of Study visit.

A by-subject listing of all EQ-5D-5L measures and the EQ VAS will be presented by visit.

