Descriptive statistics, including 95% CIs for the mean, for the PSQI Global Score will be presented for actual values and change from Baseline for scheduled visits. The change from Baseline difference in means between each dose of MM-120 and placebo and 95% for the difference will be presented for Week 4, Week 8 and the End of Study visit. A by-subject listing of results by visit, including any unscheduled visits, will be provided for all PSQI responses and the PSQI Global Score.

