## **3** EFFICACY ANALYSIS

## 3.1 Change from Baseline in HAM-A Subscales – Somatic Anxiety and Psychic Anxiety

Two subscales will be defined from the HAM-A questionnaire.

Somatic Anxiety is defined as the sum of items 7 - 13 of the HAM-A questionnaire.

Psychic Anxiety is defined as the sum of items 1 - 6, and item 14 of the HAM-A questionnaire.

Descriptive statistics will be presented for actual values and change from Baseline for scheduled visits for the FAS and PPS analysis populations. The change from Baseline will be analyzed using an analysis of covariance (ANCOVA) model including change from Baseline HAM-A Somatic Anxiety, or Psychic Anxiety, score as dependent variable, the baseline HAM-A Somatic Anxiety, or Psychic Anxiety, score as a covariate and treatment group as a fixed effect. The Least Square Means (LS Means) for each treatment group compared to placebo will be reported along with associated 95% CI and p-value. The ANCOVA comparisons will be performed for Week 1, Week 2, Week 4, Week 8 and the End of Study visit and will be presented for both the FAS and PPS populations.

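### Seven secondary scales are compared by unadjusted change from Baseline although each baseline is collected, which costs precision and leaves chance imbalance uncorrected

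*SAP*

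**What the plan says.** SAP 6.3.2 (MADRS), 6.3.3 (CGI-S) and 6.3.5 (PGI-S) report the difference in mean change between each dose and placebo, its 95% CI and a t-test: "corresponding p value from a two-sample t-test will be presented for Week 1" for MADRS, "corresponding p value from a two-sample t-test will be presented for Day 2" for CGI-S and "corresponding p-value from a two-sample t-test will be presented for Day 2" for PGI-S, each continuing to End of Study.

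SAP 6.3.7 to 6.3.10 give an unadjusted difference and interval without a p-value:
- SDS: "difference in means between each dose of MM-120 and placebo and 95% CI for the difference", with the same form for ASEX Total Score
- EQ-5D-5L index and VAS: "difference in means between each dose of MM-120 and placebo and 95% CI for the difference in means"
- PSQI: "difference in means between each dose of MM-120 and placebo and 95% for the difference will be presented for Week 4"

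HAM-A is treated differently. SAP 6.3.1 uses ANCOVA with "the baseline HAM-A Total Score as a covariate and treatment group as a fixed effect". Addendum 3.1 does the same for the ad hoc HAM-A subscales, with "the baseline HAM-A Somatic Anxiety, or Psychic Anxiety, score as a covariate and treatment group as a fixed effect".

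The Schedule of Activities (Protocol Table 2) places all seven instruments at the Baseline visit. Neither document adds a baseline-adjusted analysis for them or explains the difference from HAM-A. CGI-I and PGI-C have no baseline value of their own and are outside this point.

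**The concern.** Comparing raw change scores fixes the regression of follow-up on baseline at a slope of 1. ANCOVA estimates that slope. When the true slope is not 1, the change score carries avoidable variance, and any baseline difference between two arms that arises by chance passes in part into the estimated effect. Protocol section 3 assigns these scales to the depression, global anxiety severity, function, quality-of-life, sleep and sexual-function objectives, with about 36 subjects per arm. SAP section 8 makes MADRS and CGI-S through Week 4 final in the top-line package. Readers will rely on the difference from placebo and its interval, so the precision of that estimate matters even without formal testing.

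**Working it through.** **Inputs from the documents.** Five arms of 36 (SAP section 9), so 36 versus 36 for each dose-placebo comparison. SAP 4.5 imputes nothing for these endpoints, so analysed numbers may be lower. The plan states no power or precision for these scales. Its only such figures are the primary MCP-Mod powers (SAP Table 6), which reproduce within 0.1 point (mean 87.4%) and do not bear on this question.

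**Assumptions.** The documents give neither rho, the correlation of baseline with follow-up, nor k, the baseline SD divided by the follow-up SD. Both are varied below.

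**Precision.** In units of follow-up variance:
- change score: 1 + k² − 2·rho·k
- ANCOVA residual: 1 − rho²
- difference between the two: (k − rho)²

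The difference is never negative. With a common slope and ignoring degrees of freedom, ANCOVA is therefore never less precise, and it ties only when rho = k. CI narrowing is 1 − √[(1 − rho²)/(1 + k² − 2·rho·k)].

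Two worked cells at rho = 0.3:
- k = 1.0: 0.91/1.40 = 0.650, square root 0.806, narrowing 19%
- k = 0.6: 0.91/1.00 = 0.910, square root 0.954, narrowing 5%

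| k | rho 0.2 | rho 0.3 | rho 0.4 | rho 0.5 |
|---|---|---|---|---|
| 1.0 | 22% | 19% | 16% | 13% |
| 0.8 | 15% | 11% | 8% | 5% |
| 0.6 | 7% | 5% | 2% | 1% |

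Simulation at 36 per arm (4,000 trials per cell; pairwise ANCOVA with 69 df against the t-test with 70 df) gave these mean CI-width ratios for rho 0.2/0.3/0.4/0.5:
- k = 1.0: 0.781/0.811/0.843/0.872
- k = 0.8: 0.859/0.892/0.924/0.952
- k = 0.6: 0.932/0.962/0.984/1.001

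At higher correlations the formula gives 7.8% (rho 0.7) and 5.1% (rho 0.8) for k = 1, and about 1% and 0% for k = 0.8. Extending the simulation to rho 0.8 gave a worst ratio of about 1.007, which is essentially break-even.

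**Imbalance.** The SE of a baseline difference between two arms is √(2/36) = 0.236 baseline SD. A difference of at least 1 SE has probability of about 0.32 for a given dose-placebo pair. A 1-SE difference shifts the unadjusted estimate by (k − rho)·0.236 follow-up SD:
- k = 1, rho 0.2/0.3/0.5: 0.19/0.17/0.12
- k = 0.6, rho 0.2/0.3/0.5: 0.09/0.07/0.02

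For scale, the largest effect assumed for the primary is 0.6 SD.

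**Why not one pooled error over five arms.** As an illustration, take a residual SD of 1 in placebo, 25 and 50 µg, and 1.3 in 100 and 200 µg. The pooled variance is (3·1 + 2·1.69)/5 = 1.276, and √1.276 = 1.13. At k = 0.6 and rho 0.2/0.3/0.5, the 25 µg versus placebo CI would be 1.05/1.08/1.12 times the t-test width under a pooled error. Under a pairwise or arm-specific fit it would be 0.93/0.95/0.99 times that width.

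**The case against.** Protocol 10.2.2.4 says these scales are analysed descriptively, with similar statistics for the difference from placebo, and a raw mean difference with a CI is just that. HAM-A is the primary and key secondary instrument, so a fuller model for it can be a deliberate choice. SAP 4.6 keeps these endpoints outside the tested sequence. All of this stands, and it limits the weight of the point. It is not a reason to prefer the less precise estimate when the covariate is already in the database.

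The size rests on assumed values, and the larger gains need k near 1. Entry requires HAM-A of at least 20, and Protocol 5.1.2 names major depressive disorder as an example of an excludable confounding condition. A narrower baseline spread is therefore plausible for MADRS, CGI-S and PGI-S, where the gain may be only a few per cent. That also stands. It affects the amount, not the direction.

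A linear baseline slope is least secure for the single-item CGI-S and PGI-S and for the bounded EQ-5D-5L index. This is a fair caution. Imbalance would also be visible, because SAP 5.4 tabulates several baselines and each section summarizes actual values by visit. Seeing an imbalance does not correct the estimate.

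Finally, copying 6.3.1 unchanged across five arms could widen some intervals if variances differ. That is right, and it is why the model needs the pairwise or unequal-variance form.

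**Conclusion.** The point holds. All seven scales are compared without baseline adjustment, the baselines are available, and no planned analysis fills the gap. The unadjusted comparison is unbiased over randomization, so no type I error problem arises and the primary and key secondary conclusions do not change. The loss is one of precision and of sensitivity to the imbalance actually observed. CIs are wider than necessary by an amount ranging from negligible to about a fifth of their width, and a 1-SE imbalance moves an estimate by 0.02 to 0.19 follow-up SD. These ranges cover rho 0.2 to 0.5 and k 0.6 to 1.0, neither of which comes from the documents. The change is worth making because its direction is favourable or neutral across the range examined, but it is an improvement to descriptive secondary results and not a threat to the trial's main inference.

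**What to change.** In SAP 6.3.2, 6.3.3, 6.3.5 and 6.3.7 to 6.3.10, report the ANCOVA difference from placebo with its 95% CI, using each scale's own baseline as covariate. Give a p-value only for the three scales where one is already planned. Fit each dose-placebo pair separately, or fit all arms with arm-specific residual variances or a robust SE. Keep the raw means and changes as descriptive output, and keep the ASEX summaries by sex at birth.

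Addendum section 1 records that its analyses were added after unblinded review of the primary endpoint. If results for these scales are already unblinded, present the adjusted estimates as a labelled supplementary analysis beside the pre-specified comparison and do not replace it.

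The cost is SAP wording and a modest adaptation of the 6.3.1 program, with no new data. Each pairwise model spends one degree of freedom and assumes a linear baseline slope. Anything added after unblinding is post hoc.

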## 6.3.3 Change from Baseline in CGI-S

The CGI-S assesses the subject's current severity of illness at the time of the assessment, as assessed by the clinician and in reference to the clinician's past experience with patients having the same diagnosis. The CGI-S consists of one investigator-completed rating ranging from 1 (normal, not at all ill) to 7 (among the most extremely ill patients); a higher score indicates a more severe illness.

Descriptive statistics, including 95% CIs for the mean, will be presented for actual values and change from Baseline for scheduled visits. The change from Baseline difference in means between each dose of MM-120 and placebo, 95% CI for the difference and corresponding p value from a two-sample t-test will be presented for Day 2, Week 1, Week 2, Week 4, Week 8 and the End of Study visit. A by-subject listing of results by visit, including any unscheduled visits, will be provided.

## 6.3.4 Post-Baseline CGI-I Assessment

The CGI-I measures the clinician's assessment of how the subject's illness has improved or worsened relative to baseline. The CGI-I consists of one investigator-completed rating ranging from 1 (very much improved since the initiation of treatment) to 7 (very much worse since the initiation of treatment), where a lower score indicates improvement, and a higher score indicates worsening.

Descriptive statistics, including 95% CIs for the mean, will be presented for actual values for scheduled visits. The difference in means between each dose of MM-120 and placebo, 95% CI for the difference and corresponding p value from a two-sample t-test will be presented for Day 2, Week 1, Week 2, Week 4, Week 8 and the End of Study visit. A by-subject listing of results by visit, including any unscheduled visits, will be provided.

## 6.3.5 Change from Baseline in PGI-S

The PGI-S measures disease severity as a patient reported outcome. The PGI-S consists of one subject-completed rating ranging from 1 (none) - 5 (very severe), where a higher score indicates a more severe illness.

Descriptive statistics, including 95% CIs for the mean, will be presented for actual values and change from Baseline for scheduled visits. The change from Baseline difference in means between each dose of MM-120 and placebo, 95% CI for the difference and corresponding p-value from a two-sample t-test will be presented for Day 2, Week 1, Week 2, Week 4, Week 8 and the End of Study visit. A by-subject listing of results by visit, including any unscheduled visits, will be provided.

## 6.3.6 Post-Baseline PGI-C Assessment

The PGI-C measures change in clinical status as a patient reported outcome. The PGI-C consists

of one subject-completed rating ranging from 1 (much better) - 5 (much worse), where a lower score indicates improvement in symptoms and a high score indicates worsening symptoms.

Descriptive statistics, including 95% CIs for the mean, will be presented for actual values for scheduled visits. The difference in means between each dose of MM-120 and placebo, 95% CI for the difference and corresponding p-value from a two-sample t-test will be presented for Day 2, Week 1, Week 2, Week 4, Week 8 and the End of Study visit. A by-subject listing of results by visit, including any unscheduled visits, will be provided.

## 6.3.7 Change from Baseline in SDS Total Score

The SDS will assess the extent to which 3 major domains (work, social life/leisure activities, and family life/home responsibilities) are functionally impaired. The SDS is a self-reported assessment with 5 questions. The Total Score is derived as the sum of the response to the first 3 questions, each ranging from 0 (not at all) to 10 (extremely). The Total Score ranges from 0-30, where a higher score indicates increased functional impairment. The last 2 questions are not included in the SDS Total Score.

Descriptive statistics, including 95% CIs for the mean, for the SDS Total Score will be presented for actual values and change from Baseline for scheduled visits. The change from Baseline difference in means between each dose of MM-120 and placebo and 95% CI for the difference will be presented for Week 1, Week 2, Week 4, Week 8 and the End of Study visit. A by-subject listing of results by visit will be provided for all SDS responses and the Total Score.

## 6.3.8 Change from Baseline in EQ-5D-5L Index Values and VAS

The EQ-5D-5L will assess health outcomes over 5 dimensions: mobility, self-care, usual activities, pain/discomfort, and anxiety/depression and the EuroQol visual analog scale (EQ VAS). Each dimension has 5 levels of response scored as: 1 = no problems, 2 = slight problems, 3 = moderate problems, 4 = severe problems, and 5 = extreme problems. The five dimensions are combined to create a 5-digit code to represent the subject's health state. An EQ-5D-5L index value will be calculated by applying a formula that attaches a weight to each level in each dimension, using the US standard value set. The index is calculated by deducting the appropriate weights from 1, the value of full health. The resulting index value is a number between 0 (equivalent to dead) and 1 (full health). Missing data will not be imputed for analysis.

The frequency and proportion of subjects reporting each level for each of the 5 dimensions will be presented by visit. Changes over time will be presented using figures to present the frequency and proportion of subjects reporting each level for each of the 5 dimensions at baseline and each post-baseline measurement.

The EQ-5D-5L index values will be summarized by descriptive statistics, including 95% CIs for the mean, for actual values and change from Baseline for scheduled visits. The change from Baseline difference in means between each dose of MM-120 and placebo and 95% CI for the difference in means will be presented for Week 4, Week 8 and the End of Study visit.

The EQ VAS will be summarized by descriptive statistics, including 95% CIs for the mean, for actual values and change from Baseline for scheduled visits. The change from Baseline difference in means between each dose of MM-120 and placebo and 95% CI for the difference in means will be presented for Week 1, Week 2, Week 4, Week 8 and the End of Study visit.

A by-subject listing of all EQ-5D-5L measures and the EQ VAS will be presented by visit.

## 6.3.9 Change from Baseline in PSQI Global Score

The PSQI will assess sleep quality and disturbances for the previous month through 19 self-rated questions and 5 questions rated by the bed partner or roommate. The self-rated questions consist of 7 components:

- Subjective sleep quality
  - Component 1 Score = Question 6 Score (0-3)
- Sleep latency
  - To calculate Component 2 Score
    - 1. Assign score to Question 2 as:
      - $\leq 15$  minutes = 0
      - 16-30 minutes = 1
      - 31-60 minutes = 2
      - > 60 minutes = 3
      - 2. Add score from Question 2 to response from Question 5a
      - 3. Assign this sum as score of:

$$0 = 0$$

$$1-2 = 1$$

$$3-4 = 2$$
  
 $5-6 = 3$ 

- Sleep duration
  - To calculate Component 3 Score, assign score as follows:
    - > 7 hours = 0
    - 6-7 hours = 1
    - 5-6 hours = 2
    - <5 hours = 3
- Habitual sleep efficiency
  - To calculate Component 4 Score
    - 1. Calculate the number of hours spent in bed (Question 3 minus Question 1)
    - 2. Calculate Habitual Sleep Efficiency (HSE) as:

$$HSE (\%) = \frac{number \ of \ hours \ slept \ \{Response \ to \ Question \ 4\}}{Number \ of \ hours \ spent \ in \ bed} \times 100$$

3. Assign score as follows:

$$>85\% = 0$$
  
75-84% = 1  
65-74% = 2  
 $< 65\% = 3$ 

- Sleep disturbance
  - To Calculate Component 5 Score:
    - 1. Add the scores from Questions 5b to 5j
    - 2. Assign score as follows:

$$0 = 0$$

$$1-9 = 1$$

$$10-18 = 2$$
  
 $19-27 = 3$ 

- Use of sleeping medication
  - Component 6 Score = response to Question 7
- Daytime dysfunction
  - To calculate Component 7 Score
    - 1. Add responses to Question 8 and Question 9
    - 2. Assign Score as follows:

$$0 = 0$$
  
 $1-2 = 1$   
 $3-4 = 2$   
 $5-6 = 3$ 

To Calculate the Global PSQI score, add the seven component scores.

Each self-rated component has a Component Score ranging from 0-3 points, which are summed to calculate the Global Score with a range of 0-21. A Global Score of 0 indicates no difficulty, and a score of 21 indicates severe difficulty in all areas.

Descriptive statistics, including 95% CIs for the mean, for the PSQI Global Score will be presented for actual values and change from Baseline for scheduled visits. The change from Baseline difference in means between each dose of MM-120 and placebo and 95% for the difference will be presented for Week 4, Week 8 and the End of Study visit. A by-subject listing of results by visit, including any unscheduled visits, will be provided for all PSQI responses and the PSQI Global Score.

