## 4.1 Analysis Quality Control Procedures

Once all the source verification is complete, all queries are resolved, and the database has been updated appropriately, the database will be locked and made available to CTI Biostatistics for final

analysis.

All SAS programs used to create analysis data sets, tables, and listings will be double programmed. The SAS outputs will be compared and the programs will be updated until the outputs match.

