## 4.5 Handling of Dropouts or Missing Data

Missing data on demographics, baseline information and safety measures will be treated as missing; no imputation is planned.

Missing or partial dates and times will be imputed for analysis purposes in a manner that imputes the most conservative date or time. Imputation methods for dates and times are described for each endpoint where applicable.

Details of missing data imputation will be specified in the analysis methods for the primary and key secondary efficacy endpoints. Subject-completed questionnaires will be considered missing if incomplete. Missing data will not be imputed for analysis of non-key secondary efficacy endpoints or safety endpoints.

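### The SAP's PSQI bands overlap at exactly 6 hours of sleep and leave gaps in sleep efficiency, so some Global Scores are ambiguous or undefined

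*SAP*

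**What the plan says.** SAP 6.3.9 sets out how each of the seven PSQI components is scored from 0 to 3.

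- Component 3 (sleep duration): more than 7 h scores 0, 6 to 7 h scores 1, 5 to 6 h scores 2, less than 5 h scores 3.
- Component 4 (sleep efficiency): the first step is "Calculate the number of hours spent in bed (Question 3 minus Question 1". The second step, "Calculate Habitual Sleep Efficiency (HSE) as", divides the hours slept (Question 4) by the hours in bed and multiplies by 100. Above 85% scores 0, 75 to 84% scores 1, 65 to 74% scores 2, below 65% scores 3. No rounding rule is given.
- Total: "To Calculate the Global PSQI score, add the seven component scores". The components are then described as scores "which are summed to calculate the Global Score with a range of 0-21".

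SAP 4.5 adds: "Missing data will not be imputed for analysis of non-key secondary efficacy endpoints or safety endpoints". Protocol 8.4.9 names the components and their 0-3 range but gives no bands. The SAP addendum (2.6) carries the SAP derivations forward unchanged.

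**The concern.** A scoring key should assign exactly one score to every possible answer. This one fails in two places: one common whole-number answer has two scores, and two intervals of efficiency have none. Because the Global Score is a plain sum, a component with two scores gives two totals, and a component with no score gives no total.

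The PSQI is the only measure assigned to the sleep objective. SAP 6.3.9 plans differences from placebo in its change from Baseline, with 95% intervals, at Week 4, Week 8 and End of Study. The schedule has one PSQI before dosing, at Baseline, so a Baseline that cannot be scored would normally remove that subject from every change summary.

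The time-in-bed step is a lesser worry of the same kind. It is written as a simple difference between two items that are presumably clock times, with nothing said about a night that starts before midnight and ends after it.

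**Working it through.** **Inputs.** All bands and formulas are those of SAP 6.3.9, applied exactly as printed.

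**1. The plan's own range.** Seven components at 0 to 3 give 7 x 0 = 0 and 7 x 3 = 21, which reproduces the SAP's 0-21. (Protocol 8.4.9 prints 1-21 for the same score. That is a separate slip and plays no part here.)

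**2. Sleep duration.**

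| Hours slept | Score(s) |
|---|---|
| 4.5 | 3 |
| 5 | 2 |
| 5.5 | 2 |
| 6 | 1 and 2 |
| 6.5 | 1 |
| 7 | 1 |
| 7.5 | 0 |

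Only exactly 6 h is ambiguous. The two readings differ by 1 point in Component 3 and so in the Global Score.

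**3. Sleep efficiency.**

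| Efficiency (%) | Score |
|---|---|
| 64.9 | 3 |
| 65 | 2 |
| 74 | 2 |
| 74.5 | none |
| 75 | 1 |
| 84 | 1 |
| 84.5 | none |
| 85 | none |
| 85.01 | 0 |

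Ordinary answers can land in the gaps: 6.75/8 h = 84.4%, 7/8.25 h = 84.8%, 8.5/10 h = 85.0%.

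**4. How wide the gaps are.** The documents give no distribution of answers, so I counted combinations on an assumed grid: 6 to 10 h in bed, at least 4 h asleep, sleep not exceeding time in bed.

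| Answers given to the nearest | Unrounded efficiency | Rounded to whole percent |
|---|---|---|
| quarter hour | 10 of 289 (3.5%) | 6 of 289 (2.1%) |
| half hour | 3 of 81 (3.7%) | 2 of 81 (2.5%) |
| whole hour | 0 of 25 | 0 of 25 |

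After rounding, every unscored case sits at 85%. Rounding also pulls in values that were scored before it: 7.25/8.5 h = 85.3% scores 0 unrounded and has no score at 85%. If the top band were 85% and above, the quarter-hour counts would be 9 of 289 unrounded and 0 of 289 rounded.

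**5. Time in bed across midnight.** This assumes that Questions 1 and 3 are bedtime and rise time on a 24-hour clock and that the subtraction is coded literally. Take bed at 23:00, up at 07:00, 6 h slept.

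- Literal: 7 - 23 = -16 h; 100 x 6/(-16) = -37.5%; below 65%, score 3.
- Elapsed: 8 h; 100 x 6/8 = 75%; score 1.

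The error is 2 points, and it is silent because a negative percentage satisfies the bottom band.

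**6. Effect on change from Baseline.** If both visits cross midnight, literal subtraction gives 3 both times. The error cancels in the change, but any true change in this component is masked. If bedtime moves across midnight, a false change appears. With 6.5 h slept each time, 23:30 to 07:00 gives 7 - 23.5 = -16.5 h, -39.4%, score 3. A night from 00:00 to 07:30 gives 7.5 h, 86.7%, score 0. That is an apparent 3-point gain, although the true efficiency is 86.7% on both nights.

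**The case against.** The best reply is that this is a shorthand key read too literally.

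- **Whole percentages.** Bands of 65-74 and 75-84 suggest that efficiency is meant to be rounded first. That would close the interior gaps, but the SAP does not say so, and 85% would still have no score. The sign on the top band might be a misread of 85% and above, since the text was machine-extracted. That cannot be ruled out, although the less-than-or-equal sign for 15 minutes survives in the same section. If it is a misread and values are rounded, no efficiency gap is left. The 6-hour overlap does not depend on either point.
- **Midnight.** A reader might infer that the SAP makes time in bed negative for everyone who retires before midnight. The documents do not support that. The quantity is named as hours in bed, which cannot be negative. The questionnaire and its clock format are not shown, and someone who sleeps and rises on the same date is unaffected. What stands is that the crossing is not specified.
- **Quality control.** SAP 4.1 says: "All SAS programs used to create analysis data sets, tables, and listings will be double programmed", and outputs are reconciled until they match. Two programmers who resolve the 6-hour tie differently would therefore be found out. Double programming would not expose two who make the same choice, and it does not say which choice is right.
- **Missing data.** A reader might infer that SAP 4.5 forces these Global Scores to be lost. It does not: a recorded answer on an unassigned band edge is a scoring ambiguity, not missing data. SAP 4.5 does not supply a score either.

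**Conclusion.** The point stands as a small defect in a stated rule. As written, SAP 6.3.9 gives two scores to 6 hours of sleep and none to efficiencies between 74% and 75% or above 84% up to 85%. The Global Score is then ambiguous by 1 point or undefined, and nothing else in the protocol, SAP or addendum repairs it. The midnight step is secondary. It is an omission that produces a wrong score only if 24-hour times are subtracted literally.

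The grid counts show that the gaps can be reached by ordinary answers. A reader might take 3.5% as the share of subjects affected, but the grid is arbitrary and whole-hour answers give none. The 2-point error in one night's score should likewise not be read as a 2-point error in the endpoint, since it can cancel in the change from Baseline.

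The consequence is confined to a secondary endpoint reported with means and intervals, without a p-value and outside the testing hierarchy. The Week 4 and Week 8 HAM-A analyses are unaffected.

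**What to change.** In SAP 6.3.9:

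1. Replace the Component 3 and Component 4 bands with contiguous, non-overlapping ones applied to unrounded values, or else state a rounding rule and make the bands exhaustive under it.
2. Confirm from the instrument's scoring key which score 6 h and 85% receive. The documents do not settle either edge, so I do not propose one.
3. Define time in bed as elapsed time from bedtime to rise time, with both converted to a 24-hour clock and the difference taken modulo 24 h. Simply adding 24 h to a negative difference is not enough if times were entered on a 12-hour clock: 7 - 11 + 24 = 20 h, and 6 h slept then gives 30%, still score 3.

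The cost is a few lines of SAP text and a check of the scoring key. If the PSQI has already been analysed, check which rules the code applied, record them, and re-score if they differ from the key.
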